For the BIS™ group, sevoflurane will be titrated to achieve a target BIS™ value of 45 – 60 during maintenance of anesthesia and a target BIS™ value of 60 – 75 beginning at the start of skin closure. In order to protect against inadequate or excessive anesthesia in the BIS™ guided group, the subject will be assessed approximately every 5 minutes for signs of anesthesia. In the event of hypertension and/or tachycardia (>20% above baseline) unexplained by surgical manipulation and or signs of autonomic or somatic responses (e.g., diaphoresis, movement) an additional dose of opioid will be administered. If that does not resolve the situation, then the anesthesiologist may alter the anesthetic concentration outside the BIS™ guidelines to assure adequate anesthesia. In the event of hypotension and/or bradycardia (>20% below baseline), fluids and/or vasopressor will be administered. If that does not resolve the situation, then the anesthesiologist may alter the anesthetic concentration outside the BIS™ guidelines. Subjects with BIS™ values that are outside of the specified range of 45 – 60 during maintenance of anesthesia for >35% of the maintenance duration will be considered a protocol deviation and the subject will be excluded from the final data analysis. The subject will be replaced by an additional enrolled subject. The excluded subject will continue to be monitored for any safety events and the clinician will ensure medical care is provided for any safety event that occurs. Data from excluded subjects will be acknowledged in the final study report but will not be included in the primary statistical analysis. The exception to this exclusion is any data that is outside of the specified range of 45 – 60 as a result of the anesthesiologist titrating sevoflurane as a result of clinical signs or cardiovascular changes defined above. The end-tidal sevoflurane concentration will be continuously recorded. Fentanyl or morphine will be administered at the discretion of the anesthesiologist, for example, 1.5 mcg/kg at induction and 0.75 mcg/kg every 30 minutes in accordance with usual clinical indications.

For the SP group, sevoflurane, fentanyl, propofol, and morphine will be administered at the discretion of the anesthesiologist for example, fentanyl and morphine at 1.5 mcg/kg at induction and 0.75 mcg/kg every 30 minutes in accordance with usual clinical indications.

Medtronic Business Restricted

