Randomization	Subjects will be randomized 1:1 within each age group and each site to one of the two groups, standard practice (SP) or BIS™ (BIS) groups.
Sample Size	The first 2 - 4 subjects at each site will be enrolled to train the site team on the new technology and to determine the quality of data collection prior to randomization (n = 16-32). They will not be randomized and will not be included in the final analysis. For the analysis, a minimum of 36 subjects are required in each age group (18 per treatment group) for a minimum of 108 qualifying data sets. Subjects with non-qualifying data sets will be rejected and replaced with a newly randomized subject. This sample size was independently powered for each of the 3 age groups based on data from a previously published study conducted by Emory University.
Planned number of sites	Eight investigational sites in the US
Inclusion/Exclusion Criteria	
Inclusion Criteria:
 
1) Pediatric Subjects (ASA PS I or II or III) aged: 4 years to 18 years scheduled for procedures with sedation where the process of assessment will not interfere with the procedure, progress, or patient care 
Exclusion Criteria:
 
1) Has severe contact allergies that may cause a reaction to standard adhesive materials found in pulse oximetry sensors, ECG electrodes, respiration monitor electrodes, or other medical sensors2) Known neurological disorder (e.g., epilepsy, the presence of a brain tumor, a history of brain surgery, hydrocephalic disorders, depression needing treatment with anti-depressive drugs, a history of brain trauma, hemiplegia, demyelinating disorders, cerebral palsy, congenital anomalies of the brain or spinal cord, or other known neurologic disorders)3) Severe developmental delay per assessment of investigator or report of parent/guardian4) Airway abnormalities5) Pregnancy; subjects of childbearing potential will have a urine screen for pregnancy before surgery6) If the process of assessment will interfere with the procedure or the progress of the procedure7) Taking psychoactive medications

Medtronic Business Restricted

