Safety Assessments	
This is a prospective, randomized, controlled study where the only change in routine management is the placement of the BIS™ monitor probe on the forehead. The choice of sedative drugs, dose, and route of administration will be based on clinical indications as judged by the attending Anesthesiologist, and it will not be changed for the study.
 
The BIS™ monitor will not be used in situations where the placement of the probe will interfere with a procedure, cause scan artifacts, or where the presence of a metal monitor is contraindicated (e.g., MRI scans). Therefore, we believe there is only a minimal increase in risks from participating in the study. This risk relates to the possibility of developing irritation to the skin at the site of placement.

	
Subjects will be monitored for Adverse Events, Serious Adverse Events, and Device-Related Adverse Events from BIS™ sensor applications throughout the BIS™ sensor removal.

Statistics	
Standard demographic information and baseline characteristics will be summarized using descriptive statistics. For safety assessments, adverse events (AEs) will be summarized using frequency counts and percentages. Descriptive statistics will be provided by severity and relationship as needed.
 
The primary analysis will be based on all evaluable data (excluding training subjects). Normality of data will be tested using the Kolmogorov-Smirnov test. Depending on whether normality assumption hold, a two group t-test or Wilcoxon rank-sum test will be used to compare between the two treatment groups. A P-value of less than 0.05 is considered statistically significant unless otherwise specified.
 
The secondary endpoints will be evaluated using the Holm-Bonferroni method to ensure the overall type I error rate is controlled at the 0.05 level.
 
Cardiovascular Variables will be summarized for both groups. The incidence of hypotension will be summarized and compared to anesthesia sedation levels.
 
The anesthetic requirements with the BIS™ value, the percentage of time during maintenance with BIS™ values within the specified ranges, and number of episodes and duration of burst suppression will be assessed for both treatment groups.
 
Additional endpoints, including PAED scale, Pain Rating Score and a subgroup analysis for subjects requiring neuromuscular blockade, will be summarized using descriptive statistics for each group and groups combined.

4. Introduction

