10.9.3.3 BIS™ Guided Group

In the BIS™ group, sevoflurane will be adjusted to achieve a target BIS™ values of 45 – 60 during maintenance of anesthesia and BIS™ values of 60 – 75 beginning of skin closure. Subjects with BIS™ values that are outside of the specified range of 45 – 60 during maintenance of anesthesia for >35% of the maintenance duration will be considered a protocol deviation and the subject will be excluded from the final data analysis and will be replaced by an additional subject. The excluded subject will continue to be monitored for any safety events and the clinical will ensure that medical care is provided should a safety event occur. Data from the excluded subject will be acknowledged in the final study report but will not be

included in the primary statistical analysis. The exception to this exclusion is any data that is outside of the specified range of 45 – 60 as a result of the anesthesiologist titrating medications as a result of clinical signs or cardiovascular changes defined above. Additionally, data points will be excluded if significant artifact is present or if the sevoflurane concentration or BIS™ value is missing.

At the completion of the surgery, and after confirmation of the return of neuromuscular function, sevoflurane will be discontinued, and discontinuation time will be recorded, and as applicable, extubation will be performed when the patients demonstrate the purposeful movement, facial grimace, or eye-opening to jaw thrust.

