If the sites are found to be significantly heterogeneous with respect to the primary endpoint, additional analyses will be conducted to further assess differences between sites in baseline and procedural variables that might contribute the differences.

Medtronic Business Restricted

Missing Data

The primary analysis will include all evaluable data and missing values will not be imputed. BIS™ values that are outside of the specified range of 45 – 60 during maintenance of anesthesia for >35% of the maintenance duration will be considered a protocol deviation and will result in an exclusion of the subject from the primary analysis. The excluded subject will be replaced, and data from all excluded subjects will be noted and discussed in the final study report. Additionally, sensitivity analysis (e.g., multiple imputation) may be performed as appropriate to assess the robustness of study results.

Additional Summaries and Considerations

Cardiovascular variables will be summarized for both treatment groups. The incidence of hypotension will be summarized and compared to anesthesia sedation levels.

The anesthetic requirements with the BIS™ value, the percentage of time during maintenance with BIS™ value within the specified ranges, and number of episodes and duration of burst suppression will be assessed for the BIS and SP groups.

Additional endpoints, including the PAED scale, PACU discharge readiness and a subgroup analysis for subjects requiring neuromuscular blockade, will be evaluated by using descriptive statistics and compared between both groups.

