7.4 Handling of Missing, Unused, and Spurious Data and Dropouts

The primary analysis will include all evaluable data and missing values will not be imputed. BIS™ values that are outside of the specified range of 45 – 60 during maintenance of anesthesia for >25% of the maintenance period will be considered a protocol deviation and will result in an exclusion of the subject from the primary analysis. The excluded subject will be replaced, and data from all excluded subjects will be noted and discussed in the final study report. Additionally, sensitivity analysis (e.g., multiple imputation) may be performed as appropriate to assess the robustness of study results.

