Upon meeting the primary endpoint, the secondary endpoints will be evaluated using the Holm-Bonferroni method. The method is a sequentially rejective multiple test procedure used to adjust multiplicity and to ensure the overall type I error rate is controlled at the 0.05 level. For statistical inferences, categorical variables will be evaluated using the Chi-square test or Fisher's exact test, and continuous variables will be evaluated using the t-test or Wilcoxon rank-sum test as appropriate.

Cardiovascular variables will be summarized for both treatment groups. The incidence of hypotension will be summarized and compared to anesthesia sedation levels.

The anesthetic requirements with the BIS™ value, the percentage of time during maintenance with BIS™ value within the specified ranges, and number of episodes and duration of burst suppression will be assessed for the BIS and SP groups.

Additional endpoints, including the PAED scale, PACU discharge readiness, Anesthesia Airway Management, and a subgroup analysis for subjects requiring neuromuscular blockade, will be evaluated by using descriptive statistics and compared between BIS and SP groups.

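### The plan does not settle whether time in BIS range and burst suppression are summarised after the out-of-range exclusion; if so, the BIS arm alone is selected on the variable being summarised

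*Protocol*

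**What the plan says.** **The summary.** The synopsis (Statistics) plans to assess, for both arms, "the percentage of time during maintenance with BIS™ values within the specified ranges, and number of episodes and duration of burst suppression". Protocol 14.1 (Additional Summaries and Considerations) and SAP 7.9 plan the same. In the SAP's words, "the percentage of time during maintenance with BIS™ value within the specified ranges" and the "number of episodes and duration of burst suppression will be assessed for the BIS and SP groups". No analysis set is attached to it in any of the three places.

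**The exclusion, wide wording.** The synopsis (Study Design) says that being outside 45–60 "for >35% of the maintenance duration will be considered a protocol deviation and the subject will be excluded from the final data analysis". Section 10.9.3.3 has the same rule. The sample-size text adds: "Subjects with non-qualifying data sets will be rejected and replaced with a newly randomized subject". The rule appears under the BIS-group text; the standard practice section (10.9.3.2) has no counterpart.

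**The exclusion, narrow wording.** The same synopsis and 10.9.3.3 paragraphs go on to say that the excluded child's data are acknowledged in the report but kept out of the primary statistical analysis. Protocol 14.1 (Missing Data) says a breach "will result in an exclusion of the subject from the primary analysis", and SAP 7.4 says the same; neither names an arm. SAP 7.1.3 includes every eligible non-training subject, and SAP 7.2 says that data for all subjects will generally be presented.

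**The exception.** Out-of-range time that results from titration for clinical signs or cardiovascular changes does not lead to exclusion. No cap is given.

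**The limit.** Protocol 10.9.3.3 has "outside of the specified range of 45 – 60 during maintenance of anesthesia for >35% of the maintenance duration will be considered a protocol deviation". SAP 7.4 has "outside of the specified range of 45 – 60 during maintenance of anesthesia for >25% of the maintenance period will be considered a protocol deviation".

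**The concern.** The exclusion criterion is time out of range, and the summary is time in range. A programmer who follows the wide wording would tabulate the BIS arm after its low values had been removed and the standard practice arm with its full distribution. A large difference in favour of BIS guidance could then appear whether or not guidance had any effect.

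The primary objective is to characterise BIS performance, and this summary directly describes whether guided children stayed on target. Burst suppression is exposed in the same way, because the rule removes children who spent long periods below 45.

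**Working it through.** The plan gives no expected value for time in range, so there is no stated figure to reproduce.

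**1. Two readings**

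| Reading | Text that supports it | BIS-arm children summarised |
|---|---|---|
| A. Removal applies to everything | Final data analysis (synopsis, 10.9.3.3); rejected and replaced (synopsis, 14.2) | Only those within the limit, or excused |
| B. Removal applies to the primary analysis only | Later sentence in the same synopsis and 10.9.3.3 paragraphs; 14.1 Missing Data; SAP 7.4, 7.1.3, 7.2 | All eligible non-training children |

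Nothing in either document chooses between A and B for this summary.

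**2. The floor under reading A**

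Let c be the permitted out-of-range share and e the share of a child's maintenance time that is excused. The lowest time in range a retained child can have is 1 − c − e.

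- Protocol, c = 0.35: 65% at e = 0; 60% at e = 5%; 55% at 10%; 45% at 20%; 35% at 30%.
- SAP, c = 0.25: 75% at e = 0; 70%, 65%, 55% and 45% at the same values of e.
- If excused minutes also leave the denominator of the test, the Protocol floor is 0.65 × (1 − e): 58.5% at e = 10% and 52.0% at e = 20%.

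The documents do not say which way excused time is handled, and they give no figure for e.

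**3. Illustration of the size under reading A, with e = 0**

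Inputs from Protocol 4.1.3.2, Table 2 (children aged 3–18), maintenance BIS: standard practice 39.6 ± 11.5; BIS-guided 47.2 ± 10.1. I treat these SDs as the spread of child means. The within-child SD, w, is **assumed**, because the documents do not give it.

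For a child with mean M, time in range is p(M) = Φ((60 − M)/w) − Φ((45 − M)/w). The child is retained if p(M) ≥ 0.65, and p is averaged over M ~ Normal(mean, SD).

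For example, with w = 5, p(M) ≥ 0.65 requires M between about 47.0 and 58.0. With standard practice values the retained share is Φ((58.0 − 39.6)/11.5) − Φ((47.0 − 39.6)/11.5) = Φ(1.60) − Φ(0.64), or about 21%.

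| w | No guidance effect (39.6 ± 11.5): all children | Retained share | Mean among retained | BIS-guided values (47.2 ± 10.1): all children | Retained share | Mean among retained |
|---|---|---|---|---|---|---|
| 4 | 28% | 22% | 84% | 46% | 39% | 85% |
| 5 | 28% | 21% | 79% | 45% | 37% | 79% |
| 6 | 28% | 18% | 74% | 44% | 33% | 74% |
| 7 | 28% | 14% | 69% | 42% | 25% | 69% |
| 10 | 27% | none | – | 38% | none | – |

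- With no guidance effect, the apparent gap at w = 4 to 6 is 84 − 28 = 56 down to 74 − 28 = 46 points.
- The retained means are almost the same in the two scenarios (79.1% against 79.4% at w = 5), so the selected summary hardly separates guidance that works from guidance that does not.
- Under the SAP's 25% limit with no guidance effect, the retained means are 88%, 83% and 78% at w = 4, 5 and 6.

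**4. Burst suppression**

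In the no-effect case, time below 45 is 66–67% among all children and 11–15% among those retained (w = 4 to 6). Removal therefore takes out mostly deep records, although it also takes out children who sat above 60. The documents give no burst-suppression rates and no BIS level at which it occurs, so nothing beyond the direction can be derived.

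**The case against.** The strongest case on the other side has five parts.

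- **No text says the summary is computed after removal.** The paragraphs with the wide wording themselves end on the primary analysis, SAP 7.1.3 and 7.2 lean towards keeping everyone, and Protocol section 14 refers data exclusion to a Data Management Plan that is not among the documents. This stands. A reader might infer that the plan commits to the selected set; the documents do not support that. They leave the set open.
- **The 65% floor is not exact.** A reader might infer that every BIS-arm child must show at least 65% in range. The clinical-signs exception, which has no cap, rules that out (step 2). This stands too.
- **The summary is descriptive.** It is not a listed primary, secondary or exploratory endpoint, and no test or success rule uses it. Section 14.1 says it will be assessed, whereas the next group of endpoints is to be compared. This limits the priority, but figures set out for the two arms will still be read as a contrast.
- **The removals will be visible.** Each breach is a deviation, and Protocol 10.13 puts all deviations in the final report. SAP 7.1.1 tabulates disposition, and excluded children are to be noted and discussed. Under the no-effect illustration, filling 3 × 18 = 54 BIS-arm places would take about 54/0.22 ≈ 245 to 54/0.18 = 300 randomized children, which could not pass unnoticed. That is fair. But a count of removals does not restore the distribution of time in range, and nothing requires time in range to be tabulated with those children included.
- **The size depends on an assumed SD.** At w = 10 no child would qualify. The earlier study also used nitrous oxide and tonsillectomy or adenoidectomy cases. The figures show the mechanism and are not a forecast.

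**Conclusion.** The concern holds as an unsettled analysis set with a misleading result under one of its two readings. If the out-of-range exclusion is applied to these summaries, the BIS arm alone is selected on the summarised variable. Its time in range then has a floor near 65% (75% under the SAP's limit), lowered by any excused titration time, and the contrast with standard practice does not show whether guidance works.

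The illustrative size is a true 28% in both arms shown as about 74–84% in the BIS arm, with about 18–22% of children retained. It rests on Table 2's standard practice values in both arms, normal distributions, an assumed within-child SD of 4 to 6 and no excused time. For burst suppression the direction is plausible and no size can be given.

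A reader might extend this to the sevoflurane comparison. This point covers the descriptive titration summaries only and makes no claim about that test. It is worth correcting because the choice of reading could move the reported figure by tens of points and settling it takes little text.

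**What to change.** In Protocol 14.1 and SAP 7.9, state that time in range, time outside range and burst suppression are summarised by arm for all randomized non-training children with maintenance BIS data, including those removed under the out-of-range rule. Show the number removed, by age group, beside the summary. Present any version restricted to retained children only as a description of compliance, not as a BIS against standard practice contrast.

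In the same revision, reconcile the final-data-analysis wording with the primary-analysis wording, and the Protocol's 35% with the SAP's 25%. SAP section 3 says it was written against CIP 2.0, and the Protocol's version history places the change of limit at version 3.0, so the SAP probably was not updated.

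The cost is wording only. A breach can be identified only from the child's maintenance BIS record, so the data needed already exist. Conduct, sample size and the sevoflurane test are unaffected. The price is a less favourable reported BIS-arm time in range.

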4.1. Background

4.1.1. Basics of Anesthesia & Anesthetics

General anesthesia (GA) is a reversible state of controlled unconsciousness that is achieved with drugs that prevent awareness, pain, recall, distress, and movement in patients during surgery. Two critical components of general anesthesia are hypnosis and analgesia. Maintaining an adequate level of anesthesia depth is essential to the attenuation of these responses. The analgesic component may be considered as the probability of tolerance to a painful stimulus. Tolerance means the absence of a response being either a somatic response (e.g., movement, sweating, eye-opening) or a hemodynamic response (increase in heart rate or blood pressure). When the state of general anesthesia is inadequate for the level of nociceptive stimulation from surgery, the heart rate and blood pressure can increase dramatically, alerting the anesthesiologist to the possibility of increased nociception and arousal. Higher doses of anesthetic are necessary to prevent reactions to more intense surgical stimuli. This fact has suggested that different states of anesthesia fall along a continuum of depth, with deeper anesthesia eliminating reactions to stronger stimuli [2]. Thus, the anesthesiologist needs to know when a patient has reached a depth of anesthesia commensurate with an impending stimulus. The patient expects a surgical procedure to be safe and painless, with the assurance that throughout the procedure, s/he is asleep, without any perception or memory of what happened during that period.

4.1.2. EEG Monitoring in Anesthesia

Since 1939, anesthesiologists have known about changes in the electroencephalogram (EEG) that are produced by anesthetic agents [3]. Many of the changes that occur in the brain with changes in anesthetic states can be readily observed in unprocessed EEG recordings. Different behavioral and neurophysiological states induced by anesthetics are associated with varying EEG waveforms. The earliest use of the EEG in anesthesia tested the effects of barbiturates, eventually leading to the recognition of particular sequential effects shown in **Figure 1** [4, 5]. The first changes induced by barbiturates in the EEG are 20-30 Hz (initial rapid response) waves, followed by the superimposition of 5-12 Hz alpha waves. Loss of consciousness occurs just as the initial rapid response yields to the slower oscillations. Spindle bursts of 5-12 Hz become prominent, and in turn, decline as the EEG develops large polymorphic waves of 1-3 Hz. When this slow polymorphic activity becomes dominant, the patient tolerates skin incision. At still higher concentrations of barbiturates, the EEG displays periods of suppression, each terminating with “burst” of renewed activity, which contains high-frequency components. The burst gradually subsides as it leads into the next episode of suppression. This combination of alternating phases of high-amplitude and low-amplitude periods is called “burst suppression.”

Monitoring the depth of anesthesia could help the anesthesia professional avoid intraoperative awareness and ensure that an appropriate dose of anesthetic drugs is given for each patient. The lightness

Medtronic Business Restricted

of anesthesia can result in awareness with a recall of events that happen in the operating room. Anesthesia that is too deep could cause hemodynamic disturbances necessitating the use of vasoconstrictor agents, which constrict blood vessels to maintain normal blood pressure and cardiac output. Overly deep anesthesia can also result in respiratory depression requiring respiratory assistance postoperatively [3]. There is no objective scale that measures “too light” or “too deep” anesthesia. Bispectral Index (BIS™) technology monitoring uses processed EEG signals to measure sedation depth based on level of consciousness (LOC) signals. It allows anesthesia providers to titrate general anesthesia to achieve the desired LOC on the brain [3, 6]. BIS™ technology consists of a sensor, a digital signal converter, and a monitor. The sensor is placed on the patient’s forehead to pick up the electrical signals from the cerebral cortex and transfer them to the digital signal converter. BIS™ values quantify changes in the electrophysiologic state of the brain during anesthesia. Overall, a BIS™ value below 60 is associated with a low probability of response to commands. The BIS™ is a continuously processed EEG parameter that correlates to the patient’s level of hypnosis, where 100 = awake and 0 = flat-line EEG. The BIS™ parameter was designed to correlate with “hypnotic” clinical endpoints (sedation, lack of awareness, and memory) and to track changes in the effects of anesthetics on the brain. **Figure 1** reflects a general association between clinical state and BIS™ values. Ranges are based on results from a multi-center study [6] of the BIS™ system involving the administration of specific anesthetic agents. BIS™ values and ranges assume that the EEG is free of artifacts that can affect its performance. Titration of anesthetics to the BIS™ range should be dependent upon the individual goals established for each patient. These goals and associated BIS ranges may vary over time and in the context of patient status and treatment plan.

[figure not shown]

Figure 1: BIS™ Range Guidelines; a general association between clinical state and BIS™ values

